## 7 STUDY SUBJECTS

### 7.1 INCLUSION CRITERIA

1.  $\geq 18$  years of age.
2. 1) Symptomatic persistent AF refractory or intolerant to at least 1 class I or III antiarrhythmic medication Persistent AF - defined as Persistent: AF that is sustained  $> 7$  days. Episodes of AF which are terminated by electrical or pharmacologic cardioversion after  $\geq 48$  hours of AF, but prior to 7 days, should also be classified as persistent AF episodes.  
2) Planned to undergo first catheter ablation procedure ( prior atrial flutter typical is allowed)
3. Ability to understand the requirements of the study and sign the informed consent form.
4. Willingness to adhere to study restrictions and comply with all post-procedural follow-up requirements
5. Projected lifespan greater than 1 year.

### 7.2 EXCLUSION CRITERIA

1. They have baseline prolonged QT or renal failure precluding safe use of ibutilide
2. Rheumatic heart disease,
3. Current intra-cardiac thrombus,
4. History of MI or CABG within 6 weeks;
5. Class IV HF,
6. Unable to sign consent
7. Projected lifespan of  $< 1$  year
8. Women known to be pregnant or to have positive beta-HCG.
9. Participation in another study that would interfere with this study.
10. Unstable angina

11. Recent cerebral ischemic events
12. Contraindication to anticoagulation
13. Prior history of polymorphic ventricular tachycardia or torsades de pointes.

## **8 SAMPLE SIZE**

[figure not shown]
This safety and efficacy study will enroll 20 patients across 1US centers and 1 OUS center. This number has been determined on the basis of study feasibility and not by statistical means. This is a feasibility study of the mapping system (ECGi) performance in which the sample size of the clinical investigation is intended to provide preliminary estimates of safety and performance.

## **9 PATIENT ENROLLMENT AND WITHDRAWAL**

Patients meeting the study inclusion criteria will be identified in the outpatient or inpatient setting by investigators. Patients will be followed by one of the study site primary or co-investigators.

The study will typically be described (including the risks and benefits) during the initial clinic or hospital visit. Consent will typically be obtained at the time of the initial assessment if it is clear that the patient truly understands the nature of the study. Alternatively, the patient will be encouraged to take a copy of the consent form home to contemplate whether he/she would like to be enrolled in the study (see Appendix 1 for informed consent form.) Only patients who voluntarily provide consent will be included in this study. Consent will be obtained prior to undergoing the ablation procedure. Patients will be able to withdraw from the study at any point without compromising their medical care. All data will be de-identified and protected in accordance with institutional and HIPAA guidelines, including 1) de-identification of all geographic subdivisions smaller than a state; 2) all elements of dates related to the individual; 3) telephone and fax numbers; 4) email addresses; 5) social security, medical record, health plan beneficiary, account, and certificate/license numbers; 6) vehicle identifiers; 7) device identifiers; 8) URLs and IP addresses; 9) biometric identifiers; and 10) photographic images.

Eligible subjects will be consented for participation in the trial prior to undergoing AF ablation. Patients are considered enrolled once consented. Patients who do not undergo ablation within 90 days of enrolling will be considered to be screen failures. Patients will be followed for 12 months

➤ **Empiric ablation (CFAE or linear ablation) is not permitted**

## **10 STUDY PROCEDURES**

### **10.1. PRE-PROCEDURE EVALUATION**

Patients will be consented for the study in either the inpatient or outpatient setting. The following tests and procedures will occur before the ablation as a routine part of pre-procedural medical assessment:

- Recording of patient medical history (including details of previous ablation)
- Recording of patient AF/AT recurrences
- Recording medication history (including all anti-arrhythmic drugs used and duration of use)
- Obtain  $\beta$ -HCG in females of child bearing age the morning of the procedure as per usual clinical practice
- Baseline assessment of arrhythmia burden and type: Office/inpatient records, ICD interrogation report
- Collect any pre-procedural echocardiograms
- Baseline laboratory, including complete blood count, standard electrolyte panel, renal function
- Consent must be obtained before the procedure.

### **10.2 PRE-PROCEDURE MEDICATION MANAGEMENT**

Choice of pre-procedural anti-platelet and anti-thrombotic medications will be at the discretion of the primary operator. All patients will be required to have three weeks of uninterrupted anticoagulation prior to ablation. For those patients with interruptions in anticoagulation or if there is clinical concern for possible left atrial thrombus, a preprocedure transesophageal echocardiography will be performed to rule out left atrial thrombus. Typically, however, these medications will be continued through the procedure. Every effort will be made to discontinue AAD prior to ablation.

### **10.3 PROCEDURAL DETAILS**

- Patients will be brought to the electrophysiology laboratory in a fasting state
- Patients will have an ECG to determine rhythm – ie Sinus rhythm vs Atrial fibrillation
- A trained clinical specialist places 252 dry gelled ECG electrodes on the patient's torso. The CardioInsight™ Sensor Array (vest) is hooked up to the The CardioInsight™ System and body surface ECG recordings are made during the patient's arrhythmia. The patient is then sent to the

radiology department for a CT scan (no contrast) to image both the heart and electrodes on the patient's torso. A trained clinical specialist segments the CT DICOM images from the CT scan to obtain epicardial anatomy and establish heart-torso geometry. The electro grams are processed by the mapping system to produce movies of sinus rhythm activation or fibrillatory activity (both focal activity, and rotor activity) depending on presenting rhythm.

- Proper placement of vest patches will be done at this time
- Defibrillator patches will not be placed until needed

Patients will undergo electrophysiology study using a mapping system and ablation as per standard practice. Placement of trimmed patches will be placed in standardized locations

#### Ablation details

All patients undergoing ablation will be anticoagulated with heparin with the aim of maintaining ACT between 300 and 400 throughout the case. This will be confirmed with periodic ACT testing.

Ablation parameters are as per operator discretion and driver ablation will require adequate lesion placement as assessed by the operator in the area of interest as defined by the map. We recommend that ablation be performed with sufficient power and/or duration and guided by traditional parameters of effective lesion formation as confirmed by impedance drops. During atrial fibrillation additional parameters such as effacement of local electrograms or slowing of local atrial cycle length in the ablated area can be also used.

#### Other mapping and protocols

Isoprenaline challenge for trigger mapping or for induction of sustained atrial fibrillation

- The infusion can be used for doses as high at 30mcg/kg/min and should be continued for 10-30 minutes to truly assess the effect of isoprenaline. Trigger mapping requires the operators to use at least 20 mcg/kg/min or maximum tolerated dose for 10-20 minutes. When isoprenaline is used to sustain AF in cases where AF induced by pacing is nonsustained then lower doses can be used – 2-4 mcg/kg/min

AF induction and cardioversion- Induce atrial fibrillation by rapid pacing in the atrium. Once sustained AF is noted- then perform DCCV and wait to see if triggers are seen inducing atrial fibrillation.

- **Presenting rhythm- Sinus- Induce AF – is sustained >15 mins**
  - Map sinus acquired first and then Map induceAF will be acquired
- **Presenting rhythm- Atrial fibrillation**
  - Map spontAF will be acquired  
PV isolation is initially completed with standard approach
  - If AF persists then

- Progressive doses of Ibutilide should be administered (0.25mg, then 0.25mg, then 0.5mg) and repeat ECGi mapping (MapIbutilide0.25, MapIbutilide0.50 & MapIbutilide1.00) should be performed. If the rhythm organizes to atrial tachycardia this will be ablated and if rhythm converts to sinus – then procedure is deemed complete.

If still in AF, Driver regions are targeted  
(Right and left atria)

Prior to ablation- LAA and RAA cycle length are to be measured over 10 beats

Ablation of drivers can be initiated in chamber with faster CL or with greater number of identified drivers. Drivers can be addressed in order of importance as suggested by maps.

Periodic reassessment of TCL in LAA and RAA to be done to help direct operator to chamber of interest- e.g. if there is significant gradient between RAA and LAA such that RAA is faster then drivers can be pursued in RAA prior to completion of all driver regions of LA

All drivers are to be sequentially ablated; if rhythm is still not organized then ablation sites are visited again to ensure adequate ablation. If AF persists, ECGi mapping should be repeated (MapRe1,2.) and additional driver regions can be targeted

- **Ibutilide Dosing Guidelines**

1. Patients <60 kg – Ibutilide dosing is limited to a maximum dose of 0.50
2. Patients >60 kg are allowed to receive full dosing of ibutilide up to 1.0mg
3. All patients must receive 1g of intravenous magnesium to minimize the risk of ventricular arrhythmias associated with Ibutilide administration.
4. Hypokalemia and hypomagnesemia should be corrected before ibutilide infusion.
5. All aliquots must be administered over a minimum of 5 minutes.
6. If AF terminates during infusion the infusion must be terminated.
7. An EKG assessment must be done prior to any Ibutilide dosing and if QTc interval >500ms (unless on amiodarone) then further doses will not be administered.
8. Continuous ECG monitoring should be provided for at least 4 hours following ibutilide infusion or until QTc has returned to baseline.

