## PROTOCOL SUMMARY

Title:	Panoramic ECGi to guide Ablation of Non-Paroxysmal AF: Effect of Ibutilide on AF Source Location and Organization
Objective:	This prospective, multicenter observational study will examine the 1) Effect of Ibutilide on the number and size of the driver domains 2) Effect of ablation of Ibutilide-organized driver domains 3) Effect of PV isolation on driver domains
Design:	This is a prospective, multi-center, non-randomized, un-blinded, observational trial.
Enrollment:	
Eligible subjects will be consented for participation in the trial prior to undergoing AF ablation. Patients are considered eligible if they have
 
 
1. <math>\geq 18</math> years of age.
 
2.           
 
1) Symptomatic persistent AF refractory or intolerant to at least 1 class I or III antiarrhythmic medication Persistent AF - defined as Persistent: AF that is sustained <math>> 7</math> days. Episodes of AF which are terminated by electrical or pharmacologic cardioversion after <math>\geq 48</math> hours of AF, but prior to 7 days, should also be classified as persistent AF episodes.
 
2) Planned to undergo first catheter ablation procedure ( prior atrial flutter typical is allowed)
 
 
 
3. Ability to understand the requirements of the study and sign the informed consent form.
 
4. Willingness to adhere to study restrictions and comply with all post-procedural follow-up requirements
 
5. Projected lifespan greater than 1 year.
 
 
Patients will be excluded from the trial if:
 
 
1. They have baseline prolonged QT or renal failure precluding safe use of ibutilide
 
2. Rheumatic heart disease,
 
3. Current intra-cardiac thrombus,
 
4. History of MI or CABG within 6 weeks;
 
5. Class IV HF,
 
6. Unable to sign consent
 
7. Projected lifespan of <math>< 1</math> year
 
8. Women known to be pregnant or to have positive beta-HCG.
 
9. Participation in another study that would interfere with this study.
 
10. Unstable Angina
 
11. Recent cerebral ischemic events
 
12. Contraindication to anticoagulation
 
13. Prior history of polymorphic ventricular tachycardia or torsades de pointes
 
 
Patients are considered enrolled once consented. Patients who do not

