## 6 ENDPOINTS

### 6.1 Primary Endpoint

Primary Endpoints:	1. Acute Procedural Outcome Analysis: after performing procedures on the 20 patients 2. Clinical Outcome Analysis - Freedom from recurrent At/AF at 12 months
Additional Endpoints:	1. Effect of PV isolation on driver domains 2. Number/Size of drivers identified/ablated baseline 3. Percentage reduction of driver regions (site and size) after ibutilide 4. AF termination rate (to AT/SR) 5. Post-ablation inducibility of sustained AF (>5 mins) with isuprel 6. Post-ablation inducibility of AF with (>5mins) burst pacing 7. Total duration of RF ablation/ Fluro time/exposure/ procedure time

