## 17 DATA ANALYSIS

Baseline clinical characteristics (e.g. age, gender, renal function) and procedural characteristics (e.g. surface intracardiac electrogram, and imaging findings) of the patients will be collected and analyzed. All continuous variables will be performed as the mean  $\pm$  standard deviation, and all categorical variables as a percentage of the total study population.

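### Post-ablation inducibility (additional endpoints 5 and 6) is reported over the whole study population without regard to whether sinus-rhythm presenters were inducible before ablation

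*Combined protocol and SAP*

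**What the plan says.** All references are to the combined protocol and SAP.

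- **Design.** The Protocol Summary states: "This is a prospective, multi-center, non-randomized, un-blinded, observational trial". Section 8 sets 20 patients and adds: "This number has been determined on the basis of study feasibility and not by statistical means".
- **Sinus presenters are expected.** Section 10.3 has the line "Patients will have an ECG to determine rhythm – ie Sinus rhythm vs Atrial fibrillation", and its part on other mapping and protocols has a branch for them: "Presenting rhythm- Sinus- Induce AF – is sustained >15 mins". No branch covers failed induction.
- **Help with induction.** The same part foresees drug support: "When isoprenaline is used to sustain AF in cases where AF induced by pacing is nonsustained".
- **Eligibility.** Sections 7.1 and 7.2 require a history of persistent AF. They require neither AF on the day nor inducibility. The screen-failure rule in section 9 covers only patients not ablated within 90 days.
- **Endpoints.** Section 6.1 lists item 5, "Post-ablation inducibility of sustained AF (>5 mins) with isuprel", and item 6, "Post-ablation inducibility of AF with (>5mins) burst pacing". Neither has a stated denominator or baseline condition.
- **Analysis.** Section 17 is descriptive and presents "all categorical variables as a percentage of the total study population".

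**The concern.** A low post-ablation inducibility rate will naturally be read as an acute result of the ablation strategy. For a patient in AF at the start, that reading has a baseline: AF was present. For a sinus presenter it depends on whether AF could be induced before the first lesion. If it could not, a negative test afterwards says little about ablation, yet under section 17 the patient stays in the denominator and lowers the reported inducibility rate.

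With no control arm, the patient's own pre-ablation state is the only available reference, and the plan does not use it. The number of sinus presenters is neither stated nor limited. Since the study's output is a set of descriptive percentages, the choice of denominator directly changes what is reported.

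**Working it through.** **Plan's own figure.** There is none to reproduce. The 20 patients are a feasibility number, and no alpha, power or expected inducibility rate is given.

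**Step 1: effect per patient.** Let m be the number not inducible before ablation, π the true non-inducibility among all others, and r the probability that a baseline non-inducible patient is again negative afterwards. The documents give none of these.

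Rate over all 20 = (m·r + (20 − m)·π)/20, so the inflation over π is m(r − π)/20.

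- r = 1, π = 0: each such patient adds 1/20 = 5 points.
- r = 1, π = 0.5: each adds 2.5 points. With m = 4 the report shows (4 + 8)/20 = 60% (95% Clopper-Pearson interval 36.1 to 80.9), against 8/16 = 50% (24.7 to 75.3) when conditioned.
- r = 0.75, π = 0.5, m = 4: (3 + 8)/20 = 55%, so the inflation halves to 5 points.

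**Step 2: a model with imperfect retest.** Assumptions, none from the documents: induced-AF duration is lognormal with median M of 10, 30 or 60 minutes; between-patient log SD 1.5; within-patient log SD w of 0.7 or 1.2; no ablation effect; no false negatives among patients presenting in AF.

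Total SD s = √(1.5² + w²) and test-retest correlation ρ = 1.5²/s². For w = 0.7, s = 1.655 and ρ = 0.821. For w = 1.2, s = 1.921 and ρ = 0.610.

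P(post ≤ 5) = Φ((ln 5 − ln M)/s). P(both ≤ 5) comes from the bivariate normal with correlation ρ. Points over all patients = 100 × sinus share × P(both ≤ 5).

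| M (min) | w | P(post ≤ 5) | P(both ≤ 5) | Still ≤ 5 if baseline ≤ 5 | Points, 25% sinus | Points, 50% sinus |
|---|---|---|---|---|---|---|
| 10 | 0.7 | 0.338 | 0.249 | 74% | 6.2 | 12.5 |
| 10 | 1.2 | 0.359 | 0.223 | 62% | 5.6 | 11.2 |
| 30 | 0.7 | 0.140 | 0.087 | 62% | 2.2 | 4.3 |
| 30 | 1.2 | 0.175 | 0.084 | 48% | 2.1 | 4.2 |
| 60 | 0.7 | 0.067 | 0.036 | 55% | 0.9 | 1.8 |
| 60 | 1.2 | 0.098 | 0.039 | 39% | 1.0 | 1.9 |

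Example, first row: (ln 5 − ln 10)/1.655 = −0.419, Φ = 0.338; P(both ≤ 5) = 0.249; 100 × 0.25 × 0.249 = 6.2 points.

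**Step 3: what is not due to baseline status.** The difference P(post ≤ 5) − P(both ≤ 5) comes from patients who had AF longer than 5 minutes at baseline and tested short afterwards by chance. It is 26% of P(post ≤ 5) in the first row (0.088/0.338) and 61% in the last (0.059/0.098). Conditioning on baseline does not remove it: among sinus presenters with baseline AF above 5 minutes, the no-effect rate is still 13 to 21% (M = 10), 6 to 11% (M = 30) or 3 to 7% (M = 60).

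**Step 4: the two thresholds.** The baseline line uses 15 minutes and the endpoints use 5. Among patients at or below 15 minutes at baseline, the model gives 46 to 48% (M = 10), 62 to 64% (M = 30) or 71 to 72% (M = 60) with AF above 5 minutes afterwards, so they count as inducible. Failing the 15-minute line is not the same as being negative on the endpoint.

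**The case against.** A reader might infer that every sinus presenter who fails the baseline induction is already counted as a success before any lesion is placed. The documents do not support that. AF of 5 to 15 minutes fails the baseline line and is inducible by the endpoint. Induction varies between tests. Isoprenaline may be used to sustain AF, and the population has symptomatic persistent AF, so baseline failures may be few. The plan has no scoring rule and nowhere labels non-inducibility a success; section 17 is a general sentence on presentation. The baseline line reads ambiguously and may govern only the acquisition of the AF map.

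Two further points carry weight. Endpoint 5 is a drug challenge, whereas baseline induction is by rapid pacing with isoprenaline as an option, so no matched baseline exists for it. Section 10.3 also sets out no explicit post-ablation retest step, so some of these patients may never be tested.

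These arguments limit the size and certainty of the problem and shape the fix. They do not remove it: isoprenaline support has no fallback if it fails, no text conditions either endpoint on baseline status, and the only stated denominator is everyone.

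**Conclusion.** The point holds as a cheap improvement to two additional, descriptive endpoints; I rate it minor to moderate. Patients not inducible before ablation can lower the reported inducibility rate without any treatment effect.

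Under the assumed model with no ablation effect, patients with baseline AF of 5 minutes or less account for about 0.9 to 6.2 points over all patients at a 25% sinus share and 1.8 to 12.5 points at 50%. The inflation shrinks as true non-inducibility among the other patients rises. Every input is an assumption, and isoprenaline support is not modelled; it would reduce the figures.

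One might be tempted to attribute the whole no-effect rate among sinus presenters (7 to 36% across the scenarios) to the missing baseline condition. That would be wrong, since 26 to 61% of it is retest noise in patients who were inducible at baseline. Sample size and error rates are unaffected, and no stated decision depends on these endpoints.

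**What to change.** 1. Add case report form fields for the duration and method (pacing alone or with isoprenaline) of AF induced at the start in each sinus presenter.
2. For endpoint 6 (burst pacing), replace the whole-population percentage in section 17. Use tested patients who were in spontaneous AF, or had AF longer than 5 minutes induced, before ablation. Add a baseline-by-post-ablation 2×2 count for sinus presenters.
3. For endpoint 5 (isuprel), report the rate split by presenting rhythm and baseline pacing inducibility. Do not present a paired 2×2, because no isuprel baseline test is mandated.
4. List baseline non-inducible patients separately, and state how many patients were tested after ablation.
5. Reconcile the 15-minute and 5-minute definitions, and state whether the 15-minute line is a condition for mapping or a definition of inducibility.

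This needs analysis wording and a few data fields, with no additional procedure. The costs are a denominator below 20, wider intervals and probably a less favourable figure. Retest noise remains, so the 2×2 count should accompany the endpoint 6 rate.

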## 3 INTRODUCTION, RATIONALE

Beyond PV isolation, ablation strategies for non-paroxysmal AF remain controversial although several types of targets have been proposed: non-PV triggers, continuous fragmented atrial electrograms, ganglionated plexi, and linear lesions. In STAR AF-2, PV isolation (PVI) alone resulted in successful maintenance of SR in only 59% of patients with persistent AF. This clearly reveals the need for establishing strategies to address non-PV sources of AF in non-paroxysmal AF. However, in the STAR AF-2 trial, after 18 months, the freedom from recurrent AF in patients assigned to PVI alone (59%) was not improved by the addition of either CFAE ablation (49%) or linear ablation (46%),  $p=0.15$ . Thus, beyond PV isolation, there is little consensus as to what additional lesion sets one should perform.

Localized driver domains perpetuating AF have been difficult to detect with conventional techniques because of the limits of sequential temporospatial mapping, intermittent firing, and, presumably, spatial meandering of rotor-like activity. However, panoramic biatrial AF mapping using a body surface array with 252 electrodes has been used to enable activation and phase-based analysis of body surface potentials. This noninvasive “ECG imaging”(ECGi) approach has been reported able to identify driver domains that, when targeted for ablation (along with PVI), can terminate AF. And most recently, the non-

randomized prospective multicenter AFACART study (8 centers, 118 patients) revealed that for persistent AF, the combination of PVI and ablation of driver domains identified by ECGi resulted in i) acute AF termination in 66% of patients, and ii) one-year freedom from recurrent atrial arrhythmias in 83%.

The efficacy of an ablation strategy of targeting these driver domains will require a number of clinical studies: both large randomized studies and smaller mechanistic studies. To this latter point, we propose conducting an exploratory study of the use of panoramic ECGi in non-paroxysmal patients, in which the effect of pharmacological organization of driver domains will be evaluated, by the administration of progressive doses of Ibutilide.

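### No ECGi map is required between PV isolation and the first ibutilide aliquot, so in patients presenting in AF the two effects on driver domains cannot be separated

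*Combined protocol and SAP*

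**What the plan says.** Section 2 lists the effect of ibutilide on driver domains (Objective 1) and the effect of PVI on them (Objective 3) as separate aims. Section 3 presents the study as mechanistic and exploratory, in which "the effect of pharmacological organization of driver domains will be evaluated, by the administration of progressive doses of Ibutilide". Section 6.1 lists an Additional endpoint for each: the PVI effect (item 1) and the percentage fall in driver regions following ibutilide (item 3). Neither names the map it is measured against.

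For patients presenting in AF, section 10.3 (Other mapping and protocols) gives this order:

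1. Map spontAF is acquired.
2. "PV isolation is initially completed with standard approach".
3. If AF persists: "Progressive doses of Ibutilide should be administered (0.25mg, then 0.25mg, then 0.5mg) and repeat ECGi mapping". The maps are labelled by cumulative dose: 0.25, 0.50 and 1.00 mg.
4. If still in AF, driver regions are ablated.
5. "If AF persists, ECGi mapping should be repeated (MapRe1,2.) and additional driver regions can be targeted".

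Three items in the Ibutilide Dosing Guidelines also bear on the maps. For patients under 60 kg, "Ibutilide dosing is limited to a maximum dose of 0.50". Item 3 says "All patients must receive 1g of intravenous magnesium", without placing this relative to the maps. Item 7 says "An EKG assessment must be done prior to any Ibutilide dosing" and sets a QTc limit for further doses.

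Earlier in section 10.3, before the CT scan, "body surface ECG recordings are made during the" presenting arrhythmia. Whether recording continues after PVI is not stated. Table 1 in section 5 adds no map. Section 17 gives means, standard deviations and percentages, with no model and no paired-map comparison.

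**The concern.** Both objectives are before-and-after comparisons within a patient. Each needs a map immediately before and a map after the step in question. The map that would close the PVI interval and open the ibutilide interval is the same one, and it is not on the schedule.

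Without it, Objective 3 has no PVI-only comparison in any patient presenting in AF. The ibutilide endpoint has two possible references, and neither is clean. Measured from Map spontAF, it includes whatever PVI removed. Measured from the 0.25 mg map, it leaves out the first aliquot. The loss cannot be repaired within the procedure: once the first aliquot is given, a drug-free post-PVI map can no longer be obtained.

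**Working it through.** The plan states no figure to reproduce. Section 8 sets N = 20 on feasibility, and section 17 is descriptive. The check is whether the scheduled maps can identify the named effects.

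**Model.** On the raw scale (driver count or size per map, so zero drivers is allowed), let b be the level before PVI, p the change due to PVI, and d1, d2, d3 the changes due to the three aliquots.

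| Map | Expected value |
|---|---|
| Map spontAF | b |
| Map Ibutilide0.25 | b + p + d1 |
| Map Ibutilide0.50 | b + p + d1 + d2 |
| Map Ibutilide1.00 | b + p + d1 + d2 + d3 |

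**As scheduled.** There are four rows and five unknowns; the rank is 4. Adding any amount to p and subtracting it from d1 leaves every map unchanged. So:

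- Estimable: p + d1, d2 and d3.
- Not estimable: p, d1 and the total drug effect d1 + d2 + d3.
- Under 60 kg the last map and d3 drop out: rank 3 of 4, with the same two effects lost.

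MapRe does not help, because it follows driver ablation. That is also true of a patient whose first aliquot is withheld, if item 7 is read that way. If Map spontAF were instead taken after PVI, the pre-PVI map would be missing and p would still be lost.

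**With one added map (Map PVI = b + p).** Rank is 5 of 5, or 4 of 4 under 60 kg. Then p = Map PVI − Map spontAF, and each cumulative drug effect is that Map Ibutilide − Map PVI.

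**Magnesium.** With a separate magnesium term g, the rank with the added map is 5 of 6. If magnesium is given after Map PVI, p is clean and d1 + g stays merged. If it is given between the two maps, p + g stays merged and the drug effects are clean. Elapsed time remains in every interval.

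**Illustration (assumed counts, not trial data).** Take 8 regions at Map spontAF, 5 at 0.25 mg and 4 at 1.00 mg, with neither step adding drivers. Let m be the unseen post-PVI count. PVI effect = (8 − m)/8; first aliquot = (m − 5)/m; total ibutilide = (m − 4)/m.

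| m | PVI | First aliquot | Total ibutilide |
|---|---|---|---|
| 8 | 0% | 37.5% | 50% |
| 7 | 12.5% | 28.6% | 42.9% |
| 6 | 25% | 16.7% | 33.3% |
| 5 | 37.5% | 0% | 20% |

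Four regions are lost in all, and three of them (8 to 5) cannot be attributed by count.

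**Would a dose-response assumption settle it?** It gives an answer, but the answer depends on the assumption:

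- Linear in dose: 1 region is lost over 0.75 mg, so m = 5 + 0.25/0.75 = 5.33. PVI = 2.67/8 = 33%; ibutilide = 1.33/5.33 = 25%.
- Saturating, d/(d + 0.25): the curve is 0.5 at 0.25 mg and 0.8 at 1.00 mg. The scale is 1/(0.8 − 0.5) = 3.33, so m = 5 + 0.5 × 3.33 = 6.67. PVI = 1.33/8 = 17%; ibutilide = 2.67/6.67 = 40%.

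The plan states neither.

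**The case against.** The strongest reply is about weight. The affected endpoints are Additional, the study is exploratory and descriptive, and no test or sample size depends on them. The one stated hypothesis concerns the combined approach. All of this is true. But being exploratory excuses a small sample; it does not excuse a schedule that cannot show the quantity an objective names.

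A second reply is that Objective 1 never says against no drug, and that the 0.25 to 0.50 to 1.00 mg comparisons survive. That stands in part: Objective 1 is narrowed, whereas Objective 3 loses its comparison altogether.

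Third, the word baseline in Additional endpoint 2 suggests Map spontAF as the reference, so the percentage can be computed. It can, but it would then be a PVI-plus-drug change reported as an ibutilide effect.

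Fourth, the maps show location, and a driver lost within the isolated region points to PVI. That gives partial attribution only, since PVI may act at a distance.

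Finally, the vest is in use for the later maps, so an operator could record after PVI anyway. The documents neither require nor exclude this. A recording that nobody has to make cannot be relied on across two sites. These points limit the finding but do not remove it.

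**Conclusion.** The concern holds and should be settled before procedures begin. Followed exactly, the schedule gives 0 of up to 20 patients a required map that isolates PVI. Twenty is an upper bound, because the number who will present in AF is not given. In those patients the PVI effect and the ibutilide effect against no drug are not separable, and a larger sample would not help.

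The rank result rests only on the order of steps in section 10.3 and on treating each aliquot as its own step. The percentages rest on assumed counts and show how wide the ambiguity could be, not what this trial will find.

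The increments from 0.25 to 0.50 mg and from 0.50 to 1.00 mg, rhythm outcomes after ibutilide, the 12-month endpoint and safety reporting are not affected. Nothing is claimed about patients presenting in sinus rhythm, for whom section 10.3 does not clearly say whether the PVI and ibutilide sequence applies.

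**What to change.** In section 10.3, add one named map (Map PVI), recorded when PVI is complete, AF persists and no ibutilide has been given.

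In sections 6 and 17, define:

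- the PVI effect as Map PVI against the patient's own pre-PVI AF map;
- the ibutilide effect as each Map Ibutilide against the patient's own Map PVI, with the number of patients contributing at each cumulative dose.

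State that both contrasts apply only to patients still in AF after PVI, and that the ibutilide contrast still includes elapsed time and any magnesium given after Map PVI.

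The cost is one non-invasive recording and its processing per patient still in AF after PVI (at most 20), using the vest and CT geometry already in place, together with one protocol sentence and two definitions. The added laboratory time is not given in the documents. No dose, magnesium rule or other clinical rule changes.
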